1.6 Risk analysis

This study is considered to be a non-significant risk study based on United State Food and Drug administration (FDA) and International Standards Organization (ISO) guidelines due to the daily wear nature of the study. With the potential benefit of this study, the work is considered to be ethically justifiable. Ethical approval will be sought from the University of Manchester Senate Committee on the Ethics of Research on Human Beings (hereafter referred to as Manchester UREC). The work where practical will be conducted in accordance with the ICH Good Clinical Practice Guidelines and the international standard BS EN ISO 14155:2011 'Clinical investigation of medical devices for human subjects'.

Section 2. Resources

2.1 Subject selection

In this work 55 subjects will be dispensed contact lenses.

2.1.1 Subject withdrawal and replacement

This study includes four clinical visits. Once the study consent form is signed, the subject is considered to be enrolled on the study. Subjects who have signed the consent form, but who have not completed the dispensing visit will usually be replaced. All subject data will be included in the final analyses unless there are strong grounds for exclusion; such grounds will be detailed in the final report. At the end the study, all subjects will sign a study exit form.

2.1.2 Subject recruitment

Subjects will be recruited by one or more of following means:

1. Posting study details on The University of Manchester's 'Research Volunteers' website.
2. Correspondence to existing wearers on the Eurolens Research database of subjects.
3. Advertising through a variety of media via a format separately approved by Manchester UREC.

2.1.3 Inclusion criteria

Subjects will only be eligible for the study if:

1. They are between 18 and 40 years of age (inclusive).
2. They understand their rights as a research subject and are willing and able to sign a Statement of Informed Consent.
3. They are willing and able to follow the protocol.
4. They are an existing soft reusable spherical contact lens wearer in both eyes.
5. They have a contact lens spherical prescription between -0.50 to -6.00D (inclusive) based on the ocular refraction.
6. They have a cylindrical correction of -0.875DC or less in each eye based on the ocular refraction
7. They own a wearable pair of spectacles and wear them on the day of the initial visit.
8. They have distance high contrast logMAR visual acuity of 0.2 or better in each eye with their habitual spectacles.
9. They agree not to participate in other clinical research for the duration of the study.

2.1.4 Exclusion criteria

Subjects will not be eligible to take part in the study if:

1. They have an ocular disorder which would normally contra-indicate contact lens wear.
2. They have a systemic disorder which would normally contra-indicate contact lens wear.
3. They are using any topical medication such as eye drops or ointment.
4. They are aphakic.
5. They have had corneal refractive surgery.
6. They have any corneal distortion resulting from previous hard or rigid lens wear or have keratoconus.
7. They are pregnant or breastfeeding.
8. They have any infectious disease which would, in the opinion of the investigator, contraindicate contact lens wear or pose a risk to study personnel; or they have any immunosuppressive disease (e.g. HIV), or a history of anaphylaxis or severe allergic reaction.
9. They have taken part in any other contact lens or care solution clinical trial or research, within two weeks prior to starting this study.

2.2 Subject discontinuation

In general, subjects should be discontinued at any time, if it is in their best interests, as judged by the investigator. Reasons for this may include clinical signs of grade 3 or more, lack of motivation, discomfort, repeated refusal to follow instructions or the use of non-study products such as solutions or lenses. Subjects will be discontinued if a serious adverse event occurs or if they miss two or more planned consecutive visits. Subjects who fail to satisfy all the inclusion and exclusion criteria will be discontinued and replaced. Subjects may choose to leave the study at their own request. All discontinuations will be carefully recorded.

2.3 Safety parameters, adverse events and concurrent illnesses

The key safety parameters are the serious and significant adverse events listed in Appendix A (adverse events are classified as 'serious', 'significant' or 'non-significant'). Clinical assessment is made at the study visit(s) for these parameters. The presence of any ocular adverse event will be recorded on the eCRF and reported to the Sponsor using CVI report forms, and those ocular adverse events described as 'serious' or 'significant' will be detailed in the final report. Similarly, any concurrent illness that is likely to impact on the relevance and quality of the captured data will be noted on the case report form.

2.3.1 Investigator obligations

At all times the investigator will act in the best interest of the subject. Referral or treatment of an adverse event or other clinical finding should be initiated in the best clinical judgement of the investigator, irrespective of the participation in the clinical study.

2.3.2 Reporting obligations

In the case of a 'serious' or 'significant' adverse ocular event, the Principal Investigator will notify the Industrial Contact Person as soon as possible. Manchester UREC and any regulatory authorities will be informed as required.

2.4 Study termination

If it becomes necessary to terminate the study earlier than planned, the Industrial Contact Person will notify the Principal Investigator who will end the study with the cooperation of other staff members. Manchester UREC will be informed.

2.5 Protocol deviations and device deficiencies

Any deviations from this protocol will be recorded, and reported to the Industrial Contact Person as appropriate. Manchester UREC will be informed as necessary. Device deficiencies will be recorded and reported to the Industrial Contact Person.

2.5.1 Protocol amendments

Any amendments will be agreed between the Industrial Contact Person and the Principal Investigator with the cooperation of other staff members. Amendments will be recorded, identified and distributed. Approval from Manchester UREC will be obtained as necessary.

2.6 Study resources

Study products will be stored according to the manufacturer's product instructions.

2.6.1 Lenses

Details of the study lenses are provided in Table 2. All lens types are CE marked. Initial lens selection will be as indicated by the manufacturer fitting guidelines.

Name	Biofinity	Clariti 1 day	MyDay
Manufacturer	CooperVision Inc.	CooperVision Inc.	CooperVision Inc.
Material	comfilcon A	somofilcon A	stenfilcon A
EWC (%)	55	56	54
BOZR (mm)	8.6	8.6	8.4
Diameter (mm)	14.0	14.1	14.2
Spherical powers (D)	-0.50 to - 6.00 (0.25 steps)	-0.50 to - 6.00 (0.25 steps)	-0.50 to - 6.00 (0.25 steps)

Table 2: Study lenses.

2.6.1.1 Use of lenses

Biofinity lenses will be worn on a daily wear, reusable basis (i.e. removed at end of day and stored in the provided care system). The two daily disposable study lenses will be worn on a daily wear, daily disposable basis (i.e. removed at end of day and discarded). All lenses should be worn for a minimum of eight hours per day, five days per week. The lenses are also to be worn for a minimum of two hours before attending the follow-up visits.

2.6.2 Care regimen

Biofinity lenses will be cleaned and stored using OPTI-FREE Puremoist (Alcon Inc.). Subjects will be prohibited from using any comfort drops during the course of the study.

2.6.3 Inventory control

All study lenses will be supplied by CooperVision Inc. All worn lenses will be discarded. Unworn lenses will be returned to:

[REDACTED]

[REDACTED]

[REDACTED]

[REDACTED]

[REDACTED]

[REDACTED]

[REDACTED]

2.6.4 Clinical equipment

Clinical equipment is regularly maintained and calibrated as required. Standard operating procedures and international standards are used where appropriate.

2.7 Study control

Subjects and investigators will be masked to the study lenses – lenses will be over-labelled. Masking may be broken if deemed necessary by the Principal Investigator or Industrial Contact Person.

2.8 Documentation

Documents related to this work that require archiving will be kept by Eurolens Research for a period of 10 years after completion of the final report. The Sponsor's permission will be sought before the documents are destroyed.

2.9 Data collection and analysis

Data collected in this work will be recorded on a custom developed database and an established data trail. Data handling will include export of the study information from the clinical database into spreadsheet format for manipulation, followed by export into a statistical package for analysis. Most clinical data will be entered directly onto the electronic case report form and is considered to be source data. [REDACTED]

2.10 Study completion

The clinical phase of the study will be considered as complete when all subjects have signed the exit statement.

2.11 Confidentiality

All matters related to this work will remain confidential within Eurolens Research, the funding company and any regulatory authority (e.g. Manchester UREC). Eurolens Research will take all reasonable steps to ensure that specific lens-related information is not passed on to study participants unless this is required for clinical management of an adverse event. Personal subject information will not be made available. To cater for this, subjects will only be referred by their unique identity number in the study report. The data activities of Eurolens Research are registered with the data protection officer at The University of Manchester.

2.12 Study monitoring

In order to provide quality control and quality assurance as part of this work, the study monitor will:

1. Liaise closely with the Principal Investigator.
2. Monitor and ensure the safety of the subjects.
3. Ensure that the investigation is being conducted according to the protocol.
4. Monitor and review (or oversee review of) the study records to ensure accuracy.
5. Document their observations and make them available to relevant authorised parties (e.g. Manchester UREC).
6. Implement the Eurolens Research clinical monitoring standard operating procedure.

2.13 **Clinical trial registration**

This study will be registered with clinicaltrials.gov in accordance with section 801 of the Food and Drug Administration (FDA) Act which mandates the registration of certain clinical trials of drugs and medical devices.

Section 3. Subject management

3.1 Visit scheduling

Subjects will be required to attend four study visits. Acceptable date ranges are shown in Table 3.

Visit	Target	Allowable range
Visit 1: Dispensing Biofinity	N/A	N/A
Visit 2: Follow-up with Biofinity day and dispensing first daily disposable lens	30 days from Visit 1	21-35 days from Visit 1
Visit 3: Follow-up with first daily disposable lens and dispensing second daily disposable lens	7 days from Visit 2	7-10 days from Visit 2
Visit 4: Follow-up	7 days from Visit 3	7-10 days from Visit 3

Table 3: Visits and allowable ranges.

3.1.1 Unscheduled visits

Subjects who attend at their own volition, (or as instructed to do so by the investigator) rather than for a scheduled study visit, will be examined and the visit will be classified as 'unscheduled'. Data collected at these visits will be recorded on the clinical study database.

3.1.2 Missed visits

Subjects not attending for a visit will be contacted and encouraged to return for assessment. If two consecutive study visits are missed, the subject will be discontinued. It is expected that Eurolens Research personnel will attempt all reasonable means of communication in this event, including corresponding with the subject by letter.

3.2 Visit conduct

3.2.1 Pre-enrolment

The subject will receive a study-specific information form outlining the study at least 24 hours before the initial visit.

At a suitable time, each subject will be asked to watch a short on-line information presentation detailing study visits and procedures. They will be asked to complete several multiple-choice questions to gauge their understanding of the study. Upon successful completion of these questions, the subject will be booked to attend the initial visit. Subjects should be asked not to wear their habitual contact lenses on the day of the study visit.

3.2.2 Visit 1 Dispensing with Biofinity

Subjects should attend this visit wearing their spectacles (the visit can still go ahead if they attend wearing their contact lenses). They will then be required to sign an informed consent form prior to enrolment (Appendix C). A copy of the signed form will be issued to the subject. When the subject has signed the consent form, they are considered to be enrolled on the study.

Subjects will be instructed on the following:

- Lens handling, application and removal, where necessary.
- Use of multipurpose care regimen
- Specific study instructions, such as the importance of not using any other contact lens products.
- General contact lens information such as the management of red eyes.

The following procedures will be performed (any ocular measurement procedures outlined below will be carried out on each eye):

1. Details of the ocular and contact lens wearing history of the subject will be noted (including habitual lenses, modality, wear time and comfortable wear time).
2. Details of general health and medications will be recorded.
3. [REDACTED]
4. [REDACTED]
[REDACTED]
[REDACTED]
[REDACTED]
[REDACTED]
5. [REDACTED]
[REDACTED]
[REDACTED]
[REDACTED]
[REDACTED]
[REDACTED]
[REDACTED]

Classification	Primary signs	Secondary signs
Signs	[REDACTED]	Blepharitis Meibomian gland dysfunction Mucin balls
Scale	Efron Grading Scales (scored to nearest 0.1)	Efron Grading Scales (scored to nearest 0.1) (except mucin balls, where the number is recorded).

[REDACTED]

The presence of any ocular adverse events will be recorded [REDACTED]

6. The investigator will confirm that the subject satisfies all the inclusion and exclusion criteria. Subjects who fail to meet all the criteria at this time will usually be discontinued and replaced. If in the opinion of the investigator, the subject may be eligible at a later date, the subject may be brought back for up to one repeat visit of this type.
7. The Biofinity lenses will be fitted and allowed to settle for five minutes.
8. [REDACTED]
9. [REDACTED]
10. The subject will be asked to score the following with reference to appropriate visual analogue scales (0-100) [REDACTED]
 - Comfort
 - [REDACTED]
 - [REDACTED]
11. Lens fit will then be assessed using the following evaluations: horizontal and vertical centration, corneal coverage and movement. Normally, for an acceptable fit, centration and movement will fall within currently accepted clinical criteria [between -1 and +1 on a -2 to +2 grading scale [REDACTED]
12. [REDACTED]

14. [REDACTED]
15. The investigator will answer the following question: “The fit of the lens is acceptable?” using the following grading scale. If the grade is 3 or more, the reasons why should be stated:
1. Strongly agree
 2. Agree
 3. Neither agree not disagree
 4. Disagree
 5. Strongly disagree
16. Subjects will be given an additional spare pair of lenses (and care solution at Visit 1 only).
17. Subjects will be discharged and asked to return for a one-month follow-up visit wearing the Biofinity lenses, which need to have been worn for at least two hours. Subjects should be asked to wear their lenses for a minimum of eight hours per day, five days per week.

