Clinical investigation plan

C18-652 (EX-MKTG-100)

A clinical comparison of two daily disposable soft contact lenses

**A clinical evaluation for
CooperVision Inc.**

January 2019

Contents

Document control	3
Study summary	
Section 1. Overview	6
1.1 Background	6
1.2 Personnel	6
1.3 Study objectives	6
1.4 Study design	6
1.5 Statistical considerations	6
1.6 Risk analysis	6
Section 2. Resources	8
2.1 Subject selection	8
2.2 Subject discontinuation	9
2.3 Safety parameters, adverse events and concurrent illnesses	9
2.4 Study termination	10
2.5 Protocol deviations	10
2.6 Study resources	10
2.7 Study control	11
2.8 Documentation	12
2.9 Data collection and analysis	12
2.10 Study completion	12
2.11 Confidentiality	12
2.12 Study monitoring	12
Section 3. Subject management	14
3.1 Visit scheduling	14
3.2 Visit conduct	14
3.3 Monitoring subject compliance	20
3.4 Missing, unused and spurious data	20
Section 4. Study co-ordination	21
4.1 Document processing	21
4.2 Disclosure	21
4.3 Personnel	21

Appendices

[figure not shown]

Document control

Study title: A clinical comparison of two daily disposable soft contact lenses (C18-652) (EX-MKTG-100)

[figure not shown]
Sponsor company: CooperVision Inc.

Document type:

Document author:

Document reviewed and approved by:

Document reviewed and approved by:

Study summary

This double-masked, bilateral, direct refit study will compare the clinical performance of two daily disposable contact lenses (clariti 1day and MyDay) when fitted to existing wearers of Biofinity monthly lenses.

Fifty-five subjects will be recruited and fitted with monthly Biofinity spherical lenses at the first study visit. After a month of re-useable lens wear, all subjects will be switched into daily disposable lenses (according to the randomisation table), with each study lens worn for one week.

The following will be assessed throughout the study: [REDACTED] lens fit, lens fit acceptance, first fit success [REDACTED]

[REDACTED] lens surface, [REDACTED] and subjective response [REDACTED]

A study summary is shown in Table 1.

Visit	Procedures
Information and consent presentation Visit 1: Dispensing of Biofinity	Short on-line presentation of study aims and procedures Informed consent taken Explanation of study procedures and subject instructions Ocular and contact lens history Medical history [REDACTED] Refraction [REDACTED] Fitting of Biofinity lens [REDACTED] Lens fit [REDACTED] [REDACTED]

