1.4 Study design

This will be a randomised, double-masked, crossover study, in which 55 subjects who have been 'pre-conditioned' (i.e. fitted) with Biofinity spherical lenses for one month are switched into daily disposable lenses. Subjects will wear each daily disposable lens type for one week, in random order.

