1.5 Statistical considerations

██████████ lens surface data and subjective responses will generate data that are likely to be continuous and normally distributed. As such, these will be compared using linear regression models or other parametric methods. Subjective preferences will be compared using chi-squared tests. Lens fit data are expected to be ordinal data and assessed with non-parametric approaches. Deviations from this statistical plan will be discussed in the final report. Deviations may be necessary due to differences between the actual data distribution compared with the anticipated data distribution.

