3.2.3 Visit 2: Follow-up with Biofinity/dispensing of first daily disposable lens

Subjects should attend wearing their Biofinity lenses which should have been in situ for at least two hours. Subjects who attend without lenses in situ for at least two hours will usually be rescheduled. The following procedures will be performed (any ocular measurement procedures outlined below will be carried out on each eye):

1. Any medical or ocular issues since the last visit will be recorded.
 2. Lens wearing times since the previous visit will be recorded (hours per day, days per week and comfortable hours per day).
 3. Lens wearing time on study visit day.
 4. Retrieval of any unused lenses (and care solution at Visit 2 only).
 5. [REDACTED]
6. The subject will be asked to score the following with reference to appropriate visual analogue scales (0-100) [REDACTED]:
- Comfort after insertion
 - Comfort before removal
 - Overall comfort
 - [REDACTED]
 - [REDACTED]

- [REDACTED]
- [REDACTED]
- [REDACTED]
- [REDACTED]
- [REDACTED]
- [REDACTED]
- [REDACTED]

7. [REDACTED]

- [REDACTED]
- [REDACTED]
- [REDACTED]
- [REDACTED]
- [REDACTED]
- [REDACTED]
- [REDACTED]
- [REDACTED]
- [REDACTED]
- [REDACTED]
- [REDACTED]
- [REDACTED]
- [REDACTED]
- [REDACTED]
- [REDACTED]

8. [REDACTED]
[REDACTED]
[REDACTED]
[REDACTED]
[REDACTED]
[REDACTED]

9. Lens fit [REDACTED] assessment, as described in section 3.2.2 (including push-up).

10. The investigator will answer the following question: “The fit of the lens is acceptable?” using the following grading scale. If the grade is 3 or more, the reasons why should be stated:

- Strongly agree
- Agree
- Neither agree not disagree
- Disagree
- Strongly disagree

11. The study lenses will be removed and discarded.
12. [REDACTED]
13. The first daily disposable study lens will be fitted and allowed to settle for five minutes, according to the randomisation table [REDACTED]
14. The same procedures as for Visit 1 (section 3.2.2) steps 8-15 will be carried out.
15. [REDACTED]
16. The subject will be discharged and asked to return for a one week follow-up visit wearing the study lenses which need to been worn for at least two hours. Subjects should be asked to wear their lenses for a minimum of eight hours per day, five days per week.

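### Centration and movement are graded on a two-sided scale, but the lens-fit analysis names no quality-of-fit variable; a rank test on the recorded grades would miss misfit in both directions

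*Combined protocol and SAP*

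**What the plan says.** Lens fit covers "horizontal and vertical centration, corneal coverage and movement" (section 3.2.2, step 11). For centration and movement, the normal criterion for an acceptable fit is a grade "between -1 and +1 on a -2 to +2 grading scale". No such zone is visible for corneal coverage.

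In step 15 the investigator separately rates the statement "The fit of the lens is acceptable" from 1 (strongly agree) to 5 (strongly disagree), with reasons required at grade 3 or more.

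Both measures recur for both daily lenses. At dispensing, section 3.2.3 says "The same procedures as for Visit 1 (section 3.2.2) steps 8-15 will be carried out", and its steps 9 and 10 repeat both at follow-up. Section 3.2.4 (Visit 3) and section 3.2.5 (Visit 4) refer back to section 3.2.3.

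The Study summary lists "lens fit, lens fit acceptance, first fit success" as separate items. The design is a crossover: "Subjects will wear each daily disposable lens type for one week, in random order" (section 1.4).

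The whole visible analysis plan for these data is one sentence in section 1.5: "Lens fit data are expected to be ordinal data and assessed with non-parametric approaches".

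**The concern.** On this scale a good fit lies in the middle and a poor fit lies at either end. The grades are ordered, but the order runs from one kind of misfit through good fit to the opposite kind. Calling the data ordinal and handling them non-parametrically leads most directly to a rank comparison of the grades as recorded. That comparison asks which lens sits further toward +2. It does not ask which lens fits better.

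Suppose one lens gives more grades at both -1/-2 and +1/+2 than the other. The positive and negative within-subject differences then balance, and the test sees nothing. Lens fit is a named outcome in a trial whose aim is to compare clinical performance, so a finding of no difference could be reported for a lens that fits less well.

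A fit difference between the two lenses is plausible. Table 2 gives clariti 1 day a BOZR of 8.6 mm and a diameter of 14.1 mm, and MyDay 8.4 mm and 14.2 mm.

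**Working it through.** **Inputs from the protocol.** Scale -2 to +2 and acceptable zone -1 to +1 (section 3.2.2, step 11); paired design (section 1.4); 51 completers (section 1.5.1).

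**Assumed.** Two-sided 5% level; Wilcoxon signed-rank test; one grade per subject and lens, although the protocol grades each eye; the grade distributions below. The documents give no expected distribution.

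**No figure of the plan's own to reproduce.** The 51 was set for non-inferiority on end-of-day comfort and has nothing to do with lens fit. It serves here only as the number of pairs.

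**Step 1: why cancellation occurs.** Take grades -2, -1, 0, +1, +2 with these percentages:
- Lens A: 0/10/80/10/0
- Lens B: 5/20/50/20/5

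Mean signed grade:
- A: (-1)(0.10) + (1)(0.10) = 0
- B: (-2)(0.05) + (-1)(0.20) + (1)(0.20) + (2)(0.05) = 0

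Mean distance from 0:
- A: 0.10 + 0.10 = 0.20
- B: 2(0.05) + 0.20 + 0.20 + 2(0.05) = 0.60

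Share within -1 to +1:
- A: 10 + 80 + 10 = 100%
- B: 20 + 50 + 20 = 90%

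B's average distance from the centre is three times A's, yet the paired signed difference is symmetric about 0. A signed-rank test on it can reject only at its nominal level.

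**Step 2: simulation.** 51 pairs, 2,000 trials per scenario, within-subject latent correlation 0 and 0.5. The table gives the percentage of trials rejecting.

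| Scenario (grades -2 to +2, %) | Signed grade | Absolute grade |
|---|---|---|
| Symmetric misfit: A 0/10/80/10/0, B 5/20/50/20/5 | 4.8-5.6 | 96-98 |
| Stronger symmetric misfit: same A, B 15/20/30/20/15 | about 5 | 100 |
| Partly asymmetric misfit: same A, B 3/12/50/28/7 | 40-54 | 96-98 |
| One-direction shift: same A, B 0/2/55/35/8 | 99.6-100 | 88-91 |
| Opposite leans: A 0/40/55/5/0, B 0/5/55/40/0 | 100 | about 5 |

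**Step 3: a second pair of distributions.** A is 2/13/70/13/2 and B is 8/22/40/22/8, with independent pairs and 1,500 trials. Signed grades reject 6% and absolute grades 89%. In-range shares are 13 + 70 + 13 = 96% for A and 22 + 40 + 22 = 84% for B. An exact paired test on in-range status rejects 39%.

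**Reading.** Signed grades are blind to symmetric misfit and lose much of their power under partly asymmetric misfit. They do better than absolute grades for a one-direction shift. Absolute grades miss opposite leans. Neither variable replaces the other.

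**The case against.** A reader might infer that the plan prescribes a rank test on signed grades and is therefore wrong as written. The text does not support that. Section 1.5 names no test and no variable, and paired comparisons of categories are also non-parametric and need not cancel. Parts of section 3.2.2 are redacted around step 11, and section 3.2.3 refers to a push-up assessment that is not visible there, so some lens-fit content has been removed. That 0 is the best grade is inferred from the symmetric zone; it is not stated. All this stands. Even so, the lens-fit sentence in section 1.5, where the variable belongs, is intact and leaves the choice open.

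A reader might also infer that a significant signed result from two lenses leaning opposite ways would be a false finding. It would not: opposite leans are a real difference in fit behaviour. It becomes misleading only if reported as one lens fitting better.

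The 1-5 acceptance rating runs in one direction and cannot cancel, so a misfit large enough to change acceptability can appear there. This limits the harm. It does not make the centration and movement comparison interpretable, because acceptance is a separate global judgement listed as its own item.

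Finally, much of the absolute-grade power comes from 0 versus ±1, which the protocol accepts either way. On in-range status alone, power in step 3 is 39%. That is a fair limit on the clinical weight of the result, and it is why the in-range proportion should be shown alongside.

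**Conclusion.** The point holds as under-specification with a material consequence. For centration and movement, the most direct execution of section 1.5 compares direction of fit and has about 5% rejection when one lens misfits more in both directions. Distance from 0 would detect the same difference in about 90% of trials or more (89% to 98% for the two moderate symmetric scenarios). These percentages rest on assumed grade distributions, one grade per subject and lens, and 51 pairs. The mechanism follows from the scale, provided 0 is the best grade.

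Two stronger conclusions are not supported: that the fit result will be wrong, and that signed grades should be dropped from testing. Cancellation needs misfit in both directions, a one-direction shift is found better with signed grades (99.6-100% versus 88-91%), and the acceptance rating covers fit quality in part. Corneal coverage is outside the point. Lens fit is not the powered endpoint.

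**What to change.** In section 1.5, state that for centration (horizontal and vertical) and movement, clariti 1 day and MyDay are compared within subject by a paired rank test on two variables:
- the absolute grade, meaning distance from 0, for quality of fit;
- the signed grade, for direction of fit.

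Report the proportion of fits within the protocol's own -1 to +1 range for each lens as a supportive result. State also that a signed difference alone will not be described as one lens fitting better.

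The cost is one or two sentences and one extra secondary comparison per fit variable. No new data, visits or subjects are needed, and the 51 completers and 55 dispensed are unaffected. Fixing the variables before the data are seen also removes a choice that could otherwise change the fit conclusion.
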